11.4.4 Overall Objective Status

The overall objective status for an evaluation is determined by combining the patient's status on target lesions, target lymph nodes, non-target lesions, non-target lymph nodes, and new disease as defined in the following table:

For Patients with Measurable Disease

Target Lesions &	Nontarget Lesions &	New	Overall Objective
Target Lymph Nodes	Nontarget Lymph Nodes	Sites of Disease	Status
CR	CR	No	CR
CR	Non-CR/Non-PD	No	PR
PR	CR	No	PR
	Non-CR/Non-PD		
CR/PR	Not All Evaluated*	No	PR
SD	CR	No	SD
	Non-CR/Non-PD		
	Not All Evaluated*		
Not all Evaluated	CR	No	Not Evaluated (NE)
	Non-CR/Non-PD		
	Not All Evaluated*		
PD	Unequivocal PD	Yes or No	PD
	CR		
	Non-CR/Non-PD		
	Not All Evaluated*		
CR/PR/SD/PD/Not all Evaluated	Unequivocal PD	Yes or No	PD
CR/PR/SD/PD/Not all	CR	Yes	PD
Evaluated	Non-CR/Non-PD		
	Not All Evaluated*		

^{*} See Section 11.4.3

11.4.5 Symptomatic Deterioration

Patients with global deterioration of health status requiring discontinuation of treatment without objective evidence of disease progression at that time, and not either related to study treatment or other medical conditions, should be reported as "symptomatic deterioration" on the corresponding Case Report Form in Rave. Every effort should be made to document the objective progression even after discontinuation of treatment due to symptomatic deterioration, and radiologic imaging should continue to be collected every 12 weeks until disease progression (or start of a new anticancer therapy); see Section 5.0.

11.5 Definitions of Analysis Variables

Formal definitions of variables used in analyses can be found in the Statistical Considerations section (Section 13.0) of the protocol.

12.0 END OF TREATMENT/INTERVENTION

12.1 Duration of Treatment

Patients will receive treatment until disease progression, unacceptable toxicity, or withdrawal of consent. Patients initially randomized to placebo who experience centrally-confirmed progressive disease (PD) may elect to crossover to open-label cabozantinib; see Section 3.3 and Section 4.8.

12.1.1 CR, PR, or SD

Patients who are in CR, PR or SD will continue treatment at the highest tolerable dose until the appearance of disease progression, unacceptable toxicity, or withdrawal of consent.

After treatment is discontinued, patients will be followed per Section 12.1.3.

12.1.2 Disease Progression

Patients should be given a minimum of 3 cycles of protocol therapy.

Patients who progress on blinded therapy may be unblinded, and, if randomized to placebo, they will be allowed to crossover to open-label cabozantinib; see Section 8.3.

Document details of progression, including tumor measurements, on data forms.

Patients who progress on blinded therapy who do not crossover and patients who experience disease progression on open-label cabozantinib should be followed for survival per Section 5.0.

12.1.3 Discontinuation of Study Agent

If the patient discontinues cabozantinib/placebo due to disease progression, then the patient should crossover to open-label cabozantinib (if applicable) or the patient should be followed for survival per the Study Calendar (Section 5.0). If the patient discontinues cabozantinib/placebo for a reason other than disease progression, then the patient should be followed every 12 weeks (+/- 1 week) for progression and survival per Section 5.0.

12.2 Follow-up for Patients Who Stop Protocol Therapy

If the patient discontinues cabozantinib/placebo due to disease progression and does not crossover to open-label therapy, then the patient should be followed for survival every 6 months per the Study Calendar (Section 5.0).

If the patient discontinues open-label cabozantinib due to disease progression, then the patient should be followed for survival every 6 months per the Study Calendar (Section 5.0).

12.2.1 Withdrawal of Consent

If the patient no longer wishes to continue cabozantinib/placebo and withdraws his/her consent for protocol therapy, then the patient should be asked if he/she may be followed for disease progression and survival per Section 5.0. The reason for discontinuation and the patient's response should be documented.

If the patient no longer wishes to continue disease progression follow-up and withdraws his/her consent for follow-up, then the patient should be asked if he/she may be followed for survival per Section 5.0. The reason for discontinuation and the patient's response should be documented.

If the patient no longer wishes to continue survival follow-up and withdraws his/her consent, then no additional follow-up is required. The reason for discontinuation should be documented.

If the patient is consented to either the optional substudies or biobanking (Section 14.0) and no longer wishes to have his/her specimens collected or quality of life reported and withdraws his/her consent for future collections, then no additional collections should occur. The reason for discontinuation should be documented.

If the patient is consented to either the optional substudies or biobanking (Section 14.0) and no longer wishes to have his/her specimens biobanked for use in future research or quality of life responses analyzed and withdraws his/her consent for future use, then no future analyses should occur, and his/her related health information should no longer be collected. The reason for discontinuation should be documented.

12.2.2 Stopping Study Treatment due to Toxicity

If the patient discontinues cabozantinib/placebo due to unacceptable toxicity, then the patient should be followed for disease progression and survival per the Study Calendar in Section 5.0. The date on which the patient begins a new treatment should be recorded.

12.3 Managing Ineligible Patients and Registered Patients Who Never Receive Protocol Intervention

Definition of Ineligible Patient

A study participant who is registered to the trial but does not meet all of the eligibility criteria is deemed to be ineligible.

Follow-up for Ineligible Patients Who Continue with Protocol Treatment

Patients who are deemed ineligible after registering may continue protocol treatment, provided the treating physician, Study Chair, and Executive Officer agree there are no safety concerns if the patient continues protocol treatment. All scans, tests, and data submission are to continue as if the patient were eligible. Notification of the local IRB may be necessary per local IRB policies.

Follow-up for Ineligible Patients Who Discontinue Protocol Treatment

For patients who are deemed ineligible after registering to the trial, who start treatment, but then discontinue study treatment, the same data submission requirements are to be followed as for those patients who are eligible and who discontinue study treatment.

Follow-up for Patients Who are Registered, but Never Start Study Treatment

For all study participants who are registered to the trial but who never receive study intervention (regardless of eligibility), the follow-up requirements are as follows: Baseline, off-treatment,

and post-treatment follow up (i.e. progression and survival) data submission required. See the Data Submission Schedule accompanying the All Forms Packet.

12.4 Extraordinary Medical Circumstances

If, at any time the constraints of this protocol are detrimental to the patient's health and/or the patient no longer wishes to continue protocol therapy, protocol therapy shall be discontinued. In this event:

- Document the reason(s) for discontinuation of therapy on data forms.
- Follow the patient for protocol endpoints as required by the Study Calendar.

13.0 STATISTICAL CONSIDERATIONS

This study is a two-arm randomized, double-blinded, placebo-controlled phase III trial comparing the outcomes of treatment with 1) cabozantinib or 2) placebo in patients with advanced neuroendocrine tumors after progression on prior therapy. Patients will be separated into 2 cohorts: pancreatic NET vs. carcinoid tumors. Patients will be randomized in 2:1 fashion to either cabozantinib or placebo. The randomization will be done separately within each cohort. Efficacy analyses will be based on the intention to treat principle, and all randomized patients will be included for the analysis, i.e. patients will be assigned to the treatment group they were randomized to regardless of the actual treatment received. Analysis related to adverse events will be based on the safety population. All patients who were randomized and received any amount of protocol therapy will be considered in the safety population, and patients will be assigned to the treatment group they actually received.

13.1 Accrual Time and Study Duration

Pancreatic NET Cohort

We aim to accrue 6 patients per month for 31 months for a total of 185 patients, which translates to an accrual rate of 72 patients per year. After a minimum follow-up of 8 months, the total time to primary analysis is 3.25 years (39 months).

CALGB 80701, a randomized phase II study of everolimus and octreotide with or without bevacizumab in advanced pancreatic NET, enrolled 150 patients from October 2010-October 2012. This translates to enrollment of 6.25 patients per month on average. ECOG 2211, a randomized phase II study of temozolomide plus capecitabine versus temozolomide in advanced pancreatic NET, accrued as many as 6 patients per month. Both of these studies included a patient population that is similar to the pancreatic NET cohort in this study.

Carcinoid Tumor Cohort

We aim to accrue 6 patients per month for 35 months for a total of 210 patients, which translates to an accrual rate of 72 patients per year. After a minimum follow-up of 11 months, the total time to primary analysis is 3.8 years (46 months).

Alliance A021202 (NCT 01841736), a randomized phase II study of pazopanib versus placebo in patients with progressive carcinoid tumors, enrolled 171 patients from June 2013-October 2015. A021202 included patients similar to the carcinoid tumor cohort in this study.

13.2 Sample Size

Pancreatic NET Cohort

The best historical data available on the outcome of patients with pancreatic NET and progressive disease comes from the results of the placebo arms of the RADIANT-3 study and

the randomized study of sunitinib vs. placebo. In these studies, the progression-free survival (PFS) in patients receiving placebo was approximately 5 months.

We assume an accrual period of 2.6 years (31 months), 6 patients per month, 4.32% of dropout, minimum follow-up in all other patients of 8 months, exponential survival, and that a one-sided log-rank test for superiority will be conducted at level 0.025. We also assume PFS of 5 months for patients receiving placebo. Based on these assumptions, a sample size of 185 patients (124 in cabozantinib arm and 61 in placebo arm) will result in 149 events which are required to provide 90% power to detect a hazard ratio (HR) of 0.568 between the two treatment arms. The PFS estimate corresponding to this HR is 8.8 months.

Carcinoid Tumor Cohort

The best historical data available on the outcome of patients with carcinoid tumors and progressive disease comes from the results of the placebo arms of the RADIANT-2 and RADIANT-4 studies. In the RADIANT-2 study, the PFS according to investigator review in patients receiving placebo was 8.6 months. In the RADIANT-4 study, the PFS in patients receiving placebo was 3.9 months.

We assume an accrual period of 2.9 years (35 months), 6 patients per month, 4.286% of dropout, minimum follow-up in all other patients of 11 months, exponential survival, and that a one-sided log-rank test for superiority will be conducted at level 0.025. We also assume PFS of 7 months for patients receiving placebo. Based on these assumptions, a sample size of 210 patients (141 in cabozantinib arm and 69 in placebo arm) will result in 164 events which are required to provide 90% power to detect a hazard ratio (HR) of 0.583 between the two treatment arms. The PFS estimate for the cabozantinib corresponding to this HR is 12 months.

For Both Cohorts

The rate of PFS events and censoring will be monitored over the course of the study; if it appears that the study will not reach the requisite number of PFS events within the planned study timeframe, the protocol may be amended to increase the total sample size.

13.3 Study Endpoints

13.3.1 Primary Endpoint

For both cohorts: The primary endpoint of this trial is progression-free survival (PFS), defined as the time from randomization to the first radiographic documentation of disease progression, per RECIST 1.1 determined by retrospective independent central review (i.e. IROC; see Section 7.2.3), or death from any cause. Symptomatic deterioration alone does not constitute a PFS event. Patients who do not have a PFS event will be censored for PFS at the last disease assessment date which is prior to initiation of new anticancer therapy.

13.3.2 Secondary Endpoints

For both cohorts: overall survival, adverse events, and radiographic response rate.

Overall Survival (OS)

The secondary endpoint of this study is overall survival, defined as the time from randomization to death, from any cause. Patients who do not have an OS event will be censored for OS at the date they were last known to be alive.

Adverse Events (AEs)

CTCAE AEs and the maximum grade for each type of AE will be recorded for each patient. Similarly, scores (0-4) and the maximum score for each PRO-CTCAE item will be recorded for each patient.

Radiographic Response Rate

A secondary endpoint of this study is (confirmed) radiographic response rate, defined as the proportion of patients in each arm whose best response is either complete response (CR) or partial response (PR) prior to crossover.

13.4 Stratification

The analysis will be done separately for the pancreatic NET and carcinoid tumor cohorts and will be stratified by the stratification factors listed in Section 4.6.

13.5 Analysis Plan

13.5.1 Primary Endpoint

Treatment Efficacy Decision Rules

Interim analysis for both cohorts: Two interim analyses for futility only will be performed at the time at which 33% and 66% of the projected number of events have occurred. Gamma family spending function with parameter -6 will be used for futility boundary. The futility boundary will be considered non-binding. The specific critical p-values for declaring futility at each analysis are specified in the tables below. Specifically, at 2nd interim analysis in the pancreatic NET cohort: if p-value > 0.343, then the cabozantinib will be considered inefficacious. When progression-free survival (PFS) crosses futility boundary, the accrual will be suspended (if still ongoing), the enrolled patients will be followed per protocol, and the data will be reported.

Final analysis for both cohorts: The primary efficacy analysis will be performed at the time at which 100% of the projected number of events have occurred (149 PFS events for the pancreatic NET cohort, and 164 PFS events for the carcinoid tumor cohort). The specific critical p-values for declaring superiority or futility at each analysis are specified in the tables below. Specifically, at the final analysis for the pancreatic NET cohort: if the p-value ≤ 0.023 , then the cabozantinib will be deemed effective; if not, then the cabozantinib will be considered to have not met the criteria for efficacy. Per FDA instruction, the critical p-value of 0.023 is used for analysis, even though the statistical design has a Type I error of 0.025; therefore, we are spending 0.001 alpha for efficacy at each of the two interim analyses.

Pancreatic NET Cohort - Decision Boundary

Analysis time point (% events)	Number of events	Critical p- value for efficacy	HR for efficacy	Critical p- value for futility	HR for futility
33%	50	N/A	N/A	0.856	1.375
66%	99	N/A	N/A	0.343	0.917
100% (Final)	149	0.023*	0.711	0.023*	0.711

Carcinoid	Tumor	Cohort -	Decision	Boundary

Analysis time point (% events)	Number of events	Critical p- value for efficacy	HR for efficacy	Critical p- value for futility	HR for futility
33%	55	N/A	N/A	0.856	1.356
66%	109	N/A	N/A	0.343	0.921
100% (Final)	164	0.023*	0.723	0.023*	0.723

^{*} Alpha spending of 0.001 (for efficacy) per interim analysis (overall level = 0.025) is employed per FDA instruction.

Operating characteristics for both cohorts: The tables below show the operating characteristics assuming the PFS follows exponential survival functions, and they include the operating characteristics according to the monitoring plan outlined above. The proportion of times that: 1) the study would stop early at 1st or 2nd interim analyses due to futility of cabozantinib, and 2) the study would conclude the cabozantinib is superior to placebo at the final analysis, are tabulated by true median PFS and equivalent true hazard ratio for PFS by treatment groups.

Pancreatic NET Cohort - Operating Characteristics

True	nedian PFS		%‡ of times the study will be		%‡ of times the study will be		%‡ of times
	onths) †	True stopped early for		early for	stopped early for		that
		Hazard	futi	lity	efficacy		cabozantinib
		Ratio	1^{st}	2^{nd}	1 st	2^{nd}	is declared
Placebo	Cabozantinib		interim	interim	interim	interim	superior
			analysis	analysis	analysis	analysis	
5	8.8	0.568	0.12	1.04	NA	NA	90.89
5	8	0.625	0.36	3.4	NA	NA	77.92
5	7	0.714	1.34	10.53	NA	NA	50.15
5	6	0.833	4.61	28.04	NA	NA	18.92
5	5	1	14.47	51.1	NA	NA	2.58

[†] Although we use median PFS to illustrate each scenario, the hypothesis testing is based on the entire survival curve.

[‡] Proportions are based on 10,000 replicates in the simulation study.

			%‡ of ti	mes the	%‡ of ti	imes the	
True n	nedian PFS		study v	will be	study	will be	%‡ of times
(me	(months) †		stopped early for		stopped early for		that
		Hazard	futi	lity	efficacy		cabozantinib
		Ratio	1 st	2 nd	1 st	2^{nd}	is declared
Placebo	Cabozantinib		interim	interim	interim	interim	superior
			analysis	analysis	analysis	analysis	
7	12	0.583	0.14	1.04	NA	NA	90.67
7	11	0.636	0.38	3.23	NA	NA	78.55
7	9	0.778	2.74	18.07	NA	NA	34.02
7	8	0.875	6.47	33.6	NA	NA	12.70
7	7	1	14.25	51.63	NA	NA	2.42

[†] Although we use median PFS to illustrate each scenario, the hypothesis testing is based on the entire survival curve.

Analysis plan for both cohorts: PFS will be compared between treatment arms using the stratified log rank test at one-sided level 0.023. The stratification factors listed in Section 4.6, as collected on the OPEN Enrollment Form, will be used for the analysis. The HR for PFS will be estimated using a stratified Cox proportional hazards model, and the 95% CI for the HR will be provided. Results from an unstratified analysis will also be provided. Kaplan-Meier methodology will be used to estimate the median PFS for each treatment arm, and Kaplan-Meier curves will be produced. Brookmeyer Crowley methodology will be used to construct the 95% CI for the median PFS for each treatment arm [39].

Sensitivity analysis plan for both cohorts:

- The PFS according to investigator assessment will be used as the endpoint for a sensitivity analysis.
- For patients with a PFS event related to the results of a scan performed prior to the time of scheduled restaging, the PFS event will be dated on the date of the next scheduled radiology restaging assessment.

Carcinoid Tumor Cohort – Pre-planned Subgroup Analysis

In the carcinoid tumor cohort, we will perform the subgroup analysis by the subgroups specific below to evaluate whether the treatment effect is consistent across different subgroups. Interaction p-value (interaction between treatment arms and specific subgroups) will be used to determine whether the treatment effect is consistent. A p-value of < 0.1 will indicate that there is a differential treatment effect across different subgroups.

The pre-planned subgroups are:

- Prior Anti-VEGF Therapy: Yes vs. No
- Prior Targeted Radionucleotide Therapy (PRRT): Yes vs. No

[‡] Proportions are based on 10,000 replicates in the simulation study.

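### Carcinoid subgroup analysis: one interaction p-value with a 0.1 cut-off decides consistency, but at 164 events a non-significant result does not show it

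*Combined protocol and SAP*

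**What the plan says.** Section 13.5.1, under the pre-planned subgroup analysis for the carcinoid cohort, names two factors: "Prior Anti-VEGF Therapy: Yes vs. No" and "Prior Targeted Radionucleotide Therapy (PRRT): Yes vs. No". The criterion is: "Interaction p-value (interaction between treatment arms and specific subgroups) will be used to determine whether the treatment effect is consistent". The decision sentence follows: "A p-value of < 0.1 will indicate that there is a differential treatment effect across different subgroups".

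The subgroup text gives no sidedness for the test, no expected subgroup shares, no power, and no allowance for making two tests. It does not say that subgroup HRs, the ratio of HRs or any interval will be reported. For the overall PFS comparison, the same section does ask for a stratified Cox HR with a 95% CI.

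The cohort is sized in Section 13.2 for the overall effect only: "a sample size of 210 patients (141 in cabozantinib arm and 69 in placebo arm) will result in 164 events", these being "required to provide 90% power to detect a hazard ratio (HR) of 0.583 between the two treatment arms".

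**The concern.** The plan does not spell out that p of 0.1 or more means the effect is consistent. It does say that the p-value "will be used to determine whether the treatment effect is consistent", and it offers no other criterion, so that reading follows.

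An interaction test in a trial sized for its main effect usually has low power. A non-significant result then reflects limited information as much as similar effects. Applied literally, the rule could label cabozantinib's effect consistent across prior anti-VEGF or prior PRRT when one of those subgroups gains nothing. It could also label an effect differential by chance, because the test is made twice without adjustment. A reader given only the label could not tell a tight estimate near equality from one too wide to be useful.

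**Working it through.** **Inputs.** 164 events, 210 patients (141 and 69), design HR 0.583, 90% power (Section 13.2). For the primary test, "a one-sided log-rank test for superiority will be conducted at level 0.025". Randomization is 2:1. The interaction cut-off is 0.1 (Section 13.5.1). Two inputs are assumed because the documents do not give them: a two-sided test, with one-sided as a variant, and the share f of events in the no-benefit subgroup, taken as 10% to 50%.

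**Reproducing the plan's figure.** Schoenfeld events = (1.960 + 1.282)² / [p(1−p)(ln 0.583)²]. With p = 141/210, p(1−p) = 0.2206 and (ln 0.583)² = 0.291, this gives 164. Power at 164 events is 90.1%. The design reproduces.

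**Interaction test.** With 2:1 allocation the variance of a log HR on d events is about 1/(d × 2/9) = 4.5/d. For two subgroups with shares f and 1−f:

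SE of the log ratio of HRs = √[4.5 / (164 f(1−f))]

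Power = Φ(δ/SE − c) + Φ(−δ/SE − c), with c = 1.645 for two-sided 0.1. The one-sided variant uses c = 1.282 and the first term only.

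- Scenario A: HR 1.0 in the no-benefit subgroup, 0.583 in the other. δ = −ln 0.583 = 0.540, a ratio of HRs of 1.72.
- Scenario B: the cohort-average HR (event-weighted on the log scale) stays at 0.583, so the other subgroup must have HR 0.583^(1/(1−f)).

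| Share f | SE | A, two-sided | A, one-sided | HR in the rest under B | B, two-sided |
|---|---|---|---|---|---|
| 10% | 0.552 | 26% | 38% | 0.549 | 29% |
| 20% | 0.414 | 37% | 51% | 0.509 | 49% |
| 30% | 0.361 | 44% | 58% | 0.463 | 69% |
| 50% | 0.331 | 49% | 64% | 0.340 | 95% |

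Under A, power depends on f(1−f), so 49.4% at an even split is the most that any split can give.

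**Simulation check.** 4,000 trials per scenario, exponential PFS, 35-month accrual, analysis at 164 events, a Cox model in each subgroup, with shares set by patients rather than events. Two-sided power under A was 36%, 44% and 49% at 20%, 30% and 50%. Under B it was 50%, 71% and 94%. With no interaction (30% share) the test rejected in 10.8%.

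**Precision.** The 95% interval for the ratio of HRs extends by a factor of exp(1.96 × SE) each way: 1.91, 2.03 and 2.25 at shares of 50%, 30% and 20%. At an even split, an observed ratio of exactly 1.0 would carry an interval of about 0.52 to 1.91, which still contains 1.72.

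**Events for 80% power at a ratio of 1.72.** (1.645 + 0.842)² × 4.5 / [f(1−f) × 0.291] gives about 382 (even split), 455 (30:70) or 597 (20:80), against 164 planned.

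**False alarms.** With no true interaction and independent tests, 1 − 0.9² = 19%. Without assuming independence, the chance lies between 10% (the tests always agree) and 20% (they never reject together).

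**The case against.** A reader might infer that the plan takes p below 0.1 as proof of a differential effect, and that the rule misses a no-benefit subgroup more often than it finds one. The documents support neither as a general statement. The text speaks of indication, not proof. The second claim needs three things that the documents do not supply: a two-sided test, the subgroup shares, and HR 0.583 applying outside the no-benefit subgroup. In Section 13.2, 0.583 is the HR for the whole cohort. If that average is kept, detection becomes likelier than a miss above a share of about 20%. If the test is one-sided, the same happens from about 20% upward under A. Even under A, an even split is close to a coin toss.

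Scenario A also dilutes the overall effect. At an even split the average HR is 0.583^0.5 = 0.764, and the operating characteristics in Section 13.5.1 give only 34.02% success at HR 0.778. This stands for large shares but has less force for small ones. At shares of 10% and 20% the average HR under A is 0.615 and 0.649, either side of the tabulated 0.636 with 78.55% success, and two-sided interaction power is 26% to 37%. A small prior anti-VEGF subgroup is plausible, since Section 3.2.3 lists sunitinib as qualifying therapy only for pancreatic NET, but that is an inference.

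A cut-off of 0.1 is also a conventional trade of false alarms for power, so the 19% follows from a deliberate choice and is not a fault by itself. Only two factors are pre-specified. No efficacy claim rests on them: PFS and then OS carry the formal testing. Section 2.3 separately plans to examine the primary result for consistency with other covariates. All of this stands, and it limits the point to wording and reporting.

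**Conclusion.** The point holds in a limited form. Section 13.5.1 makes one p-value the test of consistency, and at 164 events that p-value often cannot tell a subgroup with no benefit from one with the design effect. Two-sided power is about 26% to 49% if the other subgroup has HR 0.583. It is about 29% to 95% if the cohort average is held at 0.583, where the high figures require an HR well below 0.583 in the remainder (0.463 at a 30% share, 0.340 at 50%). A one-sided test in the first scenario gives about 38% to 64%. All ranges assume no-benefit shares of 10% to 50% of events. Except where power is high, p of 0.1 or more cannot be taken as consistency, and the plan gives no shares from which to judge which case applies. This is a low-cost improvement to a supportive analysis and does not affect the primary analysis.

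**What to change.** Replace the p<0.1 decision sentence in Section 13.5.1. For each level of prior anti-VEGF therapy and prior PRRT, report the number of PFS events, the HR and its 95% CI. For each factor, report the ratio of HRs with its 95% CI. The interaction p-value may stay as a descriptive quantity, stated to be two-sided. Add that p of 0.1 or more with a wide interval is inconclusive and is not evidence of consistency, and that the two tests are not adjusted for multiplicity.

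The cost is a change of SAP wording. The same Cox models serve and no new data are needed. The downside is that the analysis no longer gives a yes/no label.
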